7.1.5. Longitudinal Follow-Up Phone Calls

Subjects or their designated decision makers will be contacted by phone at 5 and 14 months following the initial ¹⁸F-AV-1451 scan to collect updated concomitant medications and medical history.

7.2. Observations and Measurements

Informed Consent

Potential subjects and legally authorized representatives, if applicable, will be allowed to read a written informed consent form. The principal investigator or designee will explain all study procedures, risks, and alternative therapies to subject. The subject will have an opportunity to have all questions answered. The appropriate parties will then sign and date the informed consent form, indicating willingness to participate in the study (see **Section 7.5**). A copy of the signed informed consent will be given to the subject or legally authorized representative.

All informed consent forms must be approved by Avid or designee, and by the appropriate Institutional Review Board (IRB) prior to use.

Medical History, Neurologic Disease History

The investigator or designee will obtain a case history at the screening visit.

- Relevant demographic information
- Review of body systems
- Social history
- Medical and surgical history
- Concurrent medications
- Neurologic Disease history (month and year of symptom onset, month and year of diagnosis, family history of neurologic disease)

Whenever possible, the medical history will be confirmed by medical records.

Physical Examination

A complete physical examination will be conducted at the screening visit. Clinically significant changes from screening will be recorded as adverse events for the relevant study period.

Neurological Examination

A neurological examination will be performed at the screening visit to evaluate cranial nerves, gait, sensory, and motor function, coordination and tendon reflexes. The investigator is to look for these specific signs:

- Pyramidal signs (plantar extension reflex, Achilles tendon clonus);
- Extrapyramidal signs (rigidity, wrist cogwheel phenomena, involuntary movements); and
- Myoclonus.

MRI

MRI, including both volumetric and standard clinical sequences will be obtained. The MRI sequences and acquisition parameters will be described in a separate document. If a comparable MRI has been performed within the last six months, for the screening MRI, and an electronic copy of the images is available for submission, it should be discussed with the sponsor whether the MRI need not be repeated.

A sub-set of subjects in the Exploratory Phase may have the option to have a rsfMRI in addition to the volumetric and standard clinical sequences at both the screening MRI and follow-up MRIs.

Electronic copies of MRI scans will be submitted to Avid or designated imaging core lab.

Vital Signs

Vital signs (pulse rate, respiratory rate, supine blood pressure) will be taken at the following time points:

- Screening visit
- Florbetapir F18 Imaging Day
 - immediately prior to injection of florbetapir F 18
- ¹⁸F-AV-1451 Imaging Day
 - Immediately prior to the administration of ¹⁸F-AV-1451 Injection
 - Within 5 minutes after completion of injection of ¹⁸F-AV-1451 Injection
 - After the completion of imaging prior to discharge

Temperature will be obtained at the following time points:

- ¹⁸F-AV-1451 Imaging Day
 - Immediately prior to the administration of ¹⁸F-AV-1451 Injection
 - After the completion of imaging prior to discharge

Height and Weight

At both the screening and imaging visits body weight will be measured, lightly clothed.

Height will be measured at screening.

Electrocardiogram

A resting 12-lead electrocardiogram will be recorded at screening. At the ¹⁸F-AV -1451 imaging visits the ECGs will be taken at the following time points:

- Two ECGs will be taken at approximately 5 minutes apart immediately prior (within approximately 10 minutes) to ¹⁸F-AV-1451 Injection administration.
- One ECG will be taken immediately (within approximately five minutes) after completion of ¹⁸F-AV -1451 injection.
- One ECG will be taken after completion of the PET scan prior to discharge.

Clinical Laboratory Tests

Clinical laboratory evaluation will be performed at screening, on imaging day: prior to administration of ¹⁸F-AV-1451 Injection, and after completion of ¹⁸F-AV-1451 imaging.

Tests will include:

- **Hematology** (5 mL EDTA): hemoglobin, hematocrit, RBC, WBC, MCH, MCHC, neutrophils, bands, lymphocytes, monocytes, eosinophils, basophils, platelets, morphology, MCV, and RBC morphology.
- **Chemistry** (6 mL blood): total bilirubin, alkaline phosphatase, ALT (SGPT), AST (SGOT), urea nitrogen, creatinine, glucose, uric acid, calcium, phosphorus, total protein, albumin, total cholesterol, triglycerides, sodium, potassium, bicarbonate, chloride, magnesium, globulin, GGT.

- **Urinalysis** (10 mL, urine): Samples will be used to assess glucose, RBC, WBC, specific gravity, pH, protein, ketones, urobilinogen, blood, nitrite, microscopic, color, bilirubin, casts, epithelial cells, leukocyte, esterase, and bacteria.
- **ApoE Genotyping** (10 mL, blood) will be performed at the initial ¹⁸F-AV-1451 imaging session for those subjects whose ApoE results are unknown.

Genetic Samples

A one-time blood collection (10 mL, blood) will be performed on the day of the initial ¹⁸F-AV-1451 imaging session for genetic analysis. Where local regulations allow, samples will be stored and analysis may be performed on genetic variants thought to play a role in dementia or related diseases. Samples will only be used for investigations related to disease and drug or class of drugs under study in the context of this clinical program. They will not be used for broad exploratory unspecified disease or population genetic analysis.

Samples will be identified by the patient number and stored for up to 15 years after the last patient visit for the study at a facility selected by the sponsor. The sample and any data generated from it can only be linked back to the patient by investigator-site personnel. Subjects may opt out of participation.

Pregnancy Testing

- **Serum beta hCG, qualitative:** performed at screening for females of childbearing potential who are not surgically sterile. A serum pregnancy test may also be obtained prior to injection at the Imaging Visit if required by the local site.
- **Urine beta hCG:** performed at both the ¹⁸F-AV-1451 and florbetapir F 18 imaging visit(s) prior to injection for females of childbearing potential (defined as pre-menopausal, less than 2 years post-menopausal or not surgically sterile).

Ohio State University Traumatic Brain Injury Identification Method (OSU TBI-ID)

Tau pathology can be associated with Traumatic Brain Injury (TBI), therefore the OSU TBI-ID (Corrigan and Bogner 2007) short version will be used to screen for a history of traumatic brain injury. It is the briefest version that still provides several summary indices on which the original version was validated. To shorten the instrument, TBIs resulting in loss of consciousness are emphasized over less severe injuries.

Mini-Mental State Examination (MMSE)

The MMSE (Folstein et al., 1975) is a brief instrument used to assess cognitive function in elderly patients. The instrument is divided into 2 sections. The first section measures orientation, memory, and attention. The maximum score for the first section is 21. The second section tests the ability of the patient to name objects, follow verbal and written commands, write a sentence, and copy figures. The maximum score for the second section is 9. The range for the total MMSE score is 0 to 30.

Alzheimer's Disease Assessment Scale—Cognitive subscale (ADAS-Cog 11)

The ADAS (ADAS-Cog; Rosen et al. 1984) was designed to assess the severity of the dysfunction in the cognitive and noncognitive behaviors characteristic of persons with AD. The cognitive subscale of the ADAS, the ADAS-Cog₁₁, consists of 11 items assessing areas of function most typically impaired in AD: orientation, verbal memory, language, and praxis. The scale ranges from 0 to 70, with higher scores indicating greater disease severity.

Digit Symbol Substitution Test (DSST)

The DSST (Wechsler Adult Intelligence Scale F Revised, 1981) is a paper test of psychomotor performance in which the subject is given a key of numbers and matching symbols and a test section with numbers and empty boxes. Under each number the subject should write down the corresponding symbol as fast as possible. The score is the number of correct number-symbol matches made within the allowed time (90 seconds). The strategy to solve the DSST consists of sequential encoding and retrieval of numbers and corresponding symbols. Incidental memory, visuo-motor coordination, perceptual organization, and selective attention are key factors that determine the final score (Wechsler Adult Intelligence ScaleFRevised, 1981). The ability to sort out irrelevant information (e.g., symbols that may look alike) also impacts performance. This test has high test-retest reliability (Matarazzo and Herman, 1984).

Digit span forward and backward (Wechsler Memory Scale-Revised (WMS-R))

Digit Span is composed of two tasks administered independently of each other: Digits Forward and Digits Backward. On both tasks, the examiner reads a series of number sequences to the subject. For each Digits Forward item, the subject is required to repeat the number sequence in the same order as presented. For Digits Backward, the subject is required to repeat the number sequence in the reverse order.

Trail Making A and B

The trail making test (Reitan and Wolfson, 1985) is a test of executive function. Part A consists of 25 circles numbered 1 through 25 distributed over a sheet of paper. The subject is instructed to connect the circles by drawing a line as quickly as possible in ascending numerical order. Part B consists of 25 circles containing either numbers (1 through 13) or letters (A-L). The subject is instructed to connect the circles while alternating between numbers and letters in ascending order. The subject is timed. The time to complete Part A is a 150 second maximum and Part B is a 300 second maximum. Testing is stopped if the maximum time is reached.

Logical Memory Test, Immediate and Delayed Recall, Story A (WMS-R)

The logical memory test (Wechsler D. 1987) assesses the ability to recall a short story. Subjects are read a story and asked to recall the story immediately and after a delay.

Animal list generation

The animal list generation (Morris et al. 1989) is used to measure verbal fluency. The subject is asked to name as many animals as possible in 60 seconds.

Boston Naming Test (BNT) (30 item)

The 30 item Boston Naming Test (Kaplan, et al. 1983) is a measure of the ability to orally label 30 line drawings of objects. The objects are presented to the subject in order of frequency, from most frequent to least frequent.

American National Adult Reading Test (ANART)

ANART (Grober and Sliwinski 1991) is a measure for estimating premorbid verbal intelligence. The subject is presented with a word list and asked to pronounce the words.

Clock drawing test

The clock drawing test (Goodglass and Kaplan 1983) has two components: a command condition and a copy condition. In the command condition, the subject draws a clock according to verbal instructions. In the copy condition, the subject copies a model clock drawn at the top of a form.

Judgment of Line Orientation Test (JOLO)

The JOLO (Benton 1978) is a non-motor measure of visual perceptual ability where there is no time demand. The task asks subjects to match two lines by their angle of orientation to a test set of lines presented below the stimulus lines.

Pfeffer Functional Activities Questionnaire (FAQ), (Pfeffer et al. 1982)

Functional status is conceptualized as the “ability to perform self-care, self- maintenance and physical activities.” FAQ was developed to assess instrumental activities of daily living involving higher level functional skills such as shopping alone, writing checks, remembering appointments..etc. FAQ asks informant to rate patient’s ability using the following scoring system: Dependent = 3; Requires assistance = 2; Has difficulty but does by self = 1; Normal = 0; Never did [the activity] but could do now = 0; Never did and would have difficulty now = 1The sum scores ranges from 0-30.

Clinical Dementia Rating (CDR) Scale (Berg, 1988)

The CDR examines 6 categories of cognitive functioning domains. Each domain is scored on a scale ranging from 0 to 3 (including 0.5). A global rating of dementia can be generated from the domain scores. A CDR Sum of Boxes can be generated from the total across domains.

Physician Visit

A physician must see the subject at screening, at baseline, prior to drug administration and at study end, prior to discharge from both the ¹⁸F-AV-1451 and florbetapir F 18 imaging sessions. At this time, the physician should review all safety data and briefly examine/query the subject regarding potential adverse events or other treatment issues. A physician or physician designee can administer these assessments on the day of imaging for the florbetapir F 18 imaging session only.

Optional Cerebrospinal fluid (CSF) collection

Depending on site participation, subjects in the Exploratory Phase will be offered to consent for optional CSF collection by LP. A β , phospho-tau, and total tau will be

measured. 20 mL of CSF will be collected from each subject and divided into 1 ml conical vials. Samples will be shipped to a facility designated by the Sponsor. Samples will be identified by the patient number and stored for up to 15 years after the last patient visit for the study at a facility selected by the sponsor

7.3. Protocol for Image Collection

The sponsor will prepare and distribute a PET Imaging Manual for ¹⁸F-AV-1451 and florbetapir F 18. MRI image acquisition parameters and transmission procedures will be outlined in an MRI procedures manual.

7.4. Good Clinical Practice and Monitoring

All clinical studies performed under the direction of Avid/CRO will be conducted in accordance with applicable regulatory requirements and International Conference on Harmonization (ICH) Good Clinical Practice (GCP) and Avid/CRO Standard Operating Procedures (SOP).

This includes:

1. IRB/IEC approval: An investigation will be initiated at a study site only after the IRB/IEC for that study site has given their written approval of the protocol and informed consent;
2. Informed Consent: Study procedures will not be initiated until the subject and/or their legally authorized representative (as appropriate) signs the informed consent form;
3. Recording and monitoring of adverse events as outlined in Section 7.7.3 including the notification of study site clinical investigators, local IRBs and the FDA regarding serious adverse event;
4. Avid RP's obligation to monitor the participating center on a regular basis; and
5. The termination of a center or the trial if conditions apply, as outlined in Section 5.6.

7.5. Informed Consent and Subject Information

Potential subjects, or their legally authorized representative (as appropriate), will be allowed to read a written informed consent form. The principal investigator or designee will explain all study procedures, risks, and alternative therapies. The subject and legally authorized representative will have an opportunity to have all questions answered by a physician. The subject will then sign and date the informed consent form, indicating willingness to participate in the study.

Subjects with AD are potentially a vulnerable population with compromised mental capacity. Investigators should take extra care to evaluate a patient's ability to give consent. If the subject is capable of giving informed consent then the subject should sign on the consent line of the informed consent form. When applicable the legally authorized

representative should sign as well, indicating that they have witnessed the subject's consent, and further agree to participate as an informant.

If the subject is not capable of giving consent, consent may be given by a legally authorized representative. However, it is expected that all subjects entering this study should at least have the capacity to understand that they are engaging in a research study and should affirm that they do not object to participating, by signing on the Subject Assent line of the consent form. If the legal guardian is also the informant, the guardian must still sign the informant line of the form, indicating their own willingness to participate as an informant.

All informed consent forms must be approved by Avid or designee, and by the appropriate Institutional Review Board (IRB). No study related procedures shall be performed prior to completion of the informed consent process, and signing of the consent form. A copy of the signed informed consent should be given to the patient and/or their legally authorized representative for their records.

7.6. Documentation

¹⁸F-AV-1451 and florbetapir F 18 PET scans, as well as MRI scans, will be saved in an appropriate electronic format as specified in the imaging manuals. A copy of all scans will be saved at the site/imaging center and a copy of each will be forwarded to the sponsor or to the designated imaging core lab as described in the imaging manuals. All other data required by the protocol will be recorded in the CRF. All data in the CRF will be substantiated by "source documents," which consist of the subject's medical files, laboratory result sheets, ECG tracings, etc. All source documentation must be available to Avid and designees. Completed source documents and CRFs may need to be made available and complete for an audit by the FDA or other international regulatory authorities or Avid at any time. A ballpoint pen should be used to ensure that all copies are legible. CRFs and all other records must be filed in accordance with applicable laws and regulations (see Section 10.6)

7.7. Adverse Events (AE)

Avid's standards for recording and reporting adverse events (AEs) are to be followed regardless of applicable regulatory requirements that may be less stringent. All AEs must be fully recorded on the Adverse Event Page of the eCRF. Investigators will be instructed to report to Avid or its designee their assessment of the potential relatedness of each AE to investigational product or protocol procedure via electronic data entry. If a patient's treatment is discontinued as a result of an AE, study site personnel must clearly report to Avid or its designee via electronic data entry the circumstances and data leading to any such discontinuation of treatment. In cases where the investigator notices an unanticipated benefit to the patient, study site personnel should report "unexpected benefit" with the actual event term to Avid or its designee (for example, the complete actual term would be "unexpected benefit- sleeping longer").

Laboratory test abnormalities considered by the Investigator to be clinically relevant should be reported on the Adverse Event Page of the eCRF. Signs and symptoms of each AE should be described in detail (e.g., start and stop dates/time, severity/intensity,

relationship to investigational product, action taken, and outcome). Additionally, any clinically significant findings from laboratory evaluations, vital sign measurements, or other study procedures including those that result in a diagnosis should be reported as an AE to Avid or its designee.

7.7.1. Adverse Event Monitoring

Each patient must be carefully monitored for adverse events. This includes clinical laboratory test variables. An assessment must be made of the severity/intensity and relationship to the administration of the trial medication.

7.7.2. Adverse Event Definitions

Adverse Events

For reporting purposes, Avid will distinguish among pre-existing conditions, treatment - emergent adverse events and trial-emergent adverse events. Pre-existing conditions (i.e., undesirable experiences, signs or symptoms that begin prior to the Screening Visit) will be recorded on the medical history and/or physical exam eCRF pages. Signs and symptoms that are believed to be due to the pre-existing condition (started prior to dose of study medication) do not have to be recorded in the AEs section of the eCRF, unless there is an increase in frequency or severity. Additionally, signs or symptoms or changes in pre-existing conditions that occur outside the trial defined adverse event reporting period (e.g., between the end of the baseline/cross-sectional imaging period and the 9 month follow-up imaging period) will be recorded in medical history.

An adverse event is any untoward medical occurrence associated with the use of a drug in humans, whether or not considered drug related. For the purposes of this study, untoward medical occurrences will be considered associated with the use of ¹⁸F-AV-1451, and thus be reported as adverse events, if they occur within 48 hours after ¹⁸F-AV-1451 administration, either at baseline or at the 9 or 18 month imaging visit. Untoward medical occurrences will be considered associated with the use of Florbetapir F 18 injection, if they occur within 48 hours after Florbetapir F 18 injection administration. Adverse events associated with the use of ¹⁸F-AV-1451 or Florbetapir F 18 injection will be recorded as treatment emergent relative to the respective drug. Adverse experiences that occur after administration of either drug but outside the 48 hour reporting window will not be reported unless the investigator believes they are attributable to the drug.

In order to capture possible adverse effects of trial participation, trial-emergent adverse events will also be reported as any untoward medical occurrences occurring, during the baseline/cross-sectional imaging period but not during the 48 hour windows following the administration of ¹⁸F-AV-1451 or Florbetapir F 18 injection. For this purpose, the baseline/cross-sectional imaging period will be defined as beginning with the signing of consent and ending 48 hours after the last of the screening/baseline procedures described in sections [7.1.1 – 7.1.3](#), including (but not limited to) neuropsychological testing, MRI, ¹⁸F-AV-1451 or Florbetapir F 18 injection PET scanning and lumbar puncture.

The end of study for the purpose of adverse event reporting is defined as 48 hours after the last administration (i.e., 18 month visit or early termination visit) of ¹⁸F-AV-1451.

Serious Adverse Event (SAE)

An SAE is an AE that results in one of the following outcomes or constitutes one of the following events:

- Death;
- Initial or prolonged inpatient hospitalization (other than that required by protocol; “social hospitalization” or any hospitalization for non-medical reasons does not constitute an SAE);
- A life-threatening experience (that is, immediate risk of dying);
- Persistent or significant disability/incapacity;
- Congenital anomaly/birth defect;
- Considered significant by the investigator for any other reason.

Important medical events that may not result in death, be life-threatening, or require hospitalization may be considered serious adverse drug events when, based upon appropriate medical judgment, they may jeopardize the patient and may require medical or surgical intervention to prevent one of the outcomes listed in this definition.

Unexpected Adverse Event

An unexpected adverse event is an adverse event not previously reported or an adverse event that occurs with specificity, severity or frequency that is not consistent with the current investigator’s brochure.

Relationship to Investigational Product

Investigators will be instructed to report their assessment of the potential relatedness of each adverse event to protocol procedure, concomitant medication and/or investigational product. The assessment of the relationship of an adverse event to the administration of the investigational product is a clinical decision based on all available information at the time of the completion of the eCRF.

Intensity/Severity of an Adverse Event

In addition to assessing the relationship of the administration of the investigational product to adverse events, an assessment is required of the intensity (severity) of the event.

The following classifications should be used:

Mild:

A mild adverse event is an adverse event, usually transient in nature and generally not interfering with normal activities.

Moderate:

A moderate adverse event is an adverse event that is sufficiently discomforting to interfere with normal activities.

Severe:

A severe adverse event is an adverse event that incapacitates the subject and prevents normal activities. Note that a severe event is not necessarily a serious event. Nor must a serious event necessarily be severe.

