7.1.4. First and Second Longitudinal Follow-up Visits

Exploratory Phase: The first and second follow-up visits will consist of PET scan procedures, an MRI, cognitive assessments and updated medical history and concomitant medications. The first follow-up scan will occur 9 (+/-2) months following the subject's initial ¹⁸F-AV-1451 scan. The second follow up scan will occur 18 (+/-2) months following the initial ¹⁸F-AV-1451 scan. The cognitive assessments and MRIs should be performed +/- 30 days of each corresponding ¹⁸F-AV-1451 PET imaging visit and within

the 9 (+/-2) months window. The cognitive assessments and MRI should take place in the same 30 day window.

Confirmatory Phase Cohort: The first and second follow-up visits will consist of cognitive assessments and updated medical history and concomitant medications. The first follow-up visit will occur 9 (+/-2) months following the subject's initial ¹⁸F-AV-1451 scan. The second follow-up visit will occur 18 (+/-2) months following the initial ¹⁸F-AV-1451 scan.

Cognitive Assessments: Raters administering the below assessments will be blinded to the ¹⁸F-AV-1451 scans for subjects in the Confirmatory Cohort

- Mini Mental State Exam (MMSE);
- Alzheimer's Disease Assessment Scale- Cognitive subscale (ADAS-Cog11);
- Neuropsychological test battery (Digit Symbol Substitution Test (DSST), Digit span forward and backward ,Trail Making A and B, Logical Memory Test, Immediate and Delayed Recall Story A , Animal list generation, Boston Naming Test (BNT) (30 item), American National Adult Reading Test (ANART), Clock Drawing Test, Benton Judgment of Line Orientation test);
- Clinical Dementia Rating (CDR) Scale; For the MCI and AD groups only.
- Pfeffer Functional Activities Questionnaire (FAQ). For the MCI and AD groups only.

Magnetic Resonance Imaging (MRI) (for Exploratory Phase cohort only)

MRI, including both volumetric and standard clinical sequences, will be obtained at the first and second follow-up visits.

¹⁸F-AV-1451 PET Imaging Session (for Exploratory Phase cohort only)

The first follow-up scan will occur 9 (+/-2) months following the subject's initial ¹⁸F-AV-1451 scan. The second follow up scan will occur 18 (+/-2) months following the initial ¹⁸F-AV-1451 scan. Procedures for the longitudinal follow-up scans will be identical to the initial scan:

- A physician must see the subject prior to administration of ¹⁸F-AV-1451 Injection to determine if they are still suitable to undergo the scan;

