7.7.4. Reporting of Serious Adverse Events

Study site personnel must alert Eli Lilly or its designee of any SAE within 24 hours of their awareness of the event via a sponsor-approved method. Alerts issued via telephone are to be immediately followed with official notification on study-specific SAE forms.

Serious adverse events occurring after a subject receive a dose of investigational product will be collected until 48 hours after the dosing of the investigational product, regardless of the investigator's opinion of causation. Therefore, SAEs that occur later than 48 hours after the dosing of the investigational product are not required to be reported unless the investigator feels the events were related to either investigational product or a protocol procedure.

If a patient experiences an SAE after signing informed consent, but prior to receiving investigational product, the event will NOT be reported unless the investigator feels the event may have been caused by a protocol procedure. Previously planned (prior to signing the ICF) surgeries should not be reported as SAEs unless the underlying medical condition has worsened during the course of the study.

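### At months 9 and 18, a non-serious procedure harm outside the 48 hours after the tracer goes to medical history unless attributed to the drug, although the same harm at baseline is an adverse event

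*Protocol*

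**What the plan says.** **Treatment-emergent events.** Protocol 7.7.2 counts an untoward occurrence as an adverse event of ¹⁸F-AV-1451 (flortaucipir in the SAP) if it falls within 48 hours after "administration, either at baseline or at the 9 or 18 month imaging visit". Florbetapir has its own 48-hour window. Events after either tracer but "outside the 48 hour reporting window will not be reported unless the investigator believes they are attributable to the drug". Changes in pre-existing conditions and symptoms outside the reporting period are entered in medical history.

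**Trial-emergent events.** To pick up effects of taking part in the trial, 7.7.2 adds events that occur "during the baseline/cross-sectional imaging period but not during the 48 hour windows following the administration of" either tracer. That period is defined as "beginning with the signing of consent and ending 48 hours after the last of the screening/baseline procedures" of sections 7.1.1 to 7.1.3; MRI and lumbar puncture are named.

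**Serious events.** Under Protocol 7.7.4, serious events later than 48 hours after dosing "are not required to be reported unless the investigator feels the events were related to either investigational product or a protocol procedure".

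**Follow-up procedures.** These are in section 7.1.4, outside the sections that bound the baseline period. For the Exploratory Phase, "MRI, including both volumetric and standard clinical sequences, will be obtained at the first and second follow-up visits", and their timing is loose: "The cognitive assessments and MRIs should be performed +/- 30 days of each corresponding" tracer PET visit.

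**SAP.** Section 6.6.2 places trial-emergent events before the imaging sessions or between the florbetapir and flortaucipir sessions. It sends events during study visits to the medical history form unless the site physician relates them to the study drugs. Section 8.7.2 bases all adverse event summaries on treatment-emergent events.

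**The concern.** The protocol has a category for harm caused by trial participation, but the category stops when the baseline procedures end. From then on the only route onto the adverse event page for a non-serious event outside a tracer window is attribution to the drug. An investigator who correctly attributes an event to a follow-up MRI has, on the wording of 7.7.2, no reason to report it.

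What is at stake is comparability between visits and the quality of the record for repeat procedures. The same non-serious MRI harm would be an adverse event at baseline and a medical-history entry at month 9. Protocol 7.7.3 asks for dates, severity, relationship, action taken and outcome for adverse events. No matching requirement is stated for medical-history updates.

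**Working it through.** The plan gives no figure here to reproduce. The check sets the rules side by side and then counts the sessions exposed.

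**Step 1: where a procedure harm is recorded if it is not attributed to the drug**

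| Event | Baseline period | Month 9 or 18 |
|---|---|---|
| Non-serious, within 48 h after a tracer | Adverse event, treatment-emergent (7.7.2) | Adverse event, treatment-emergent (7.7.2) |
| Non-serious, outside 48 h | Adverse event, trial-emergent (7.7.2) | Medical history (7.7.2; SAP 6.6.2) |
| Serious, outside 48 h, related to a procedure | Reportable (7.7.4) | Reportable (7.7.4) |

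Only the second row differs by visit. It is also the only row at months 9 and 18 with no protocol-procedure route.

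**Step 2: can a follow-up procedure fall outside the window?** Yes. The MRI and cognitive tests may be 30 days before or after the scan, and the flow chart says each follow-up visit runs over several days. Anything done before the injection on the scan day also precedes the 48 hours. In addition, 7.7.2 ends adverse event reporting 48 hours after the last ¹⁸F-AV-1451 administration. A month-18 MRI done later than that comes after the stated end of reporting.

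**Step 3: sessions exposed.** From Protocol 8.1.1.1 and the synopsis, exploratory subjects aged 50 or over comprise 60 healthy volunteers, 80 with MCI and 70 with AD.

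- Subjects: 60 + 80 + 70 = 210
- Planned follow-up MRIs: 210 x 2 = 420, before dropout

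How many lie outside the 48 hours depends on scheduling, which the documents leave open. Three assumptions, taking the MRI date as the event date, show the range:

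- MRI dates uniform over the 60-day span: 2/60 = 3.3% fall inside, leaving 420 x 58/60 = 406 outside.
- Half of the MRIs done in the 48 hours after injection: 420 x 0.5 = 210 outside.
- All done in the 48 hours after injection: 0 outside.

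The 20 young volunteers have no follow-up visits, and the Confirmatory Cohort has no follow-up MRI, so neither adds to the count.

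**Step 4: would the events reach a SAP summary?** Not as written. SAP 8.7.2 plans a table by relationship to protocol procedure, but only for treatment-emergent events. Trial-emergent events, including those at baseline, enter no summary table. The section also mentions listings of adverse events relative to dosing without saying whether trial-emergent events are included.

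**The case against.** **The texts may already require recording.** Protocol 10.7 wants every adverse event on the eCRF whatever its relation to the drug. The exploratory flow chart has adverse event rows at months 9 and 18. Section 7.1.4 requires continuous monitoring during follow-up imaging sessions. Section 7.7.2 itself mentions a month-9 follow-up imaging period, which it never defines. These do point to wider recording. But 7.7.2 is where a reportable event is defined, its exclusion is explicit, and SAP 6.6.2 follows the narrow rule. What stands is that the texts conflict and sites could act differently.

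**It may be a deliberate choice.** Lumbar puncture and florbetapir occur only around baseline, so the wider net was placed where most non-tracer procedures are. That is a fair reason for extra care at baseline. It does not explain why the serious-event rule has a procedure route and the non-serious rule has none.

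**The residual harm may be minor.** The serious-event definition includes anything the investigator considers significant, and procedure-related serious events are reportable. Section 7.7 also makes clinically significant findings from study procedures adverse events, though that mainly concerns what a procedure reveals. This limits the importance of the gap and stands.

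**Stronger readings a reader might infer, which the documents do not support:**

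- *The safety-database objective is undermined.* That objective concerns the tracer. Tracer events keep a 48-hour window regardless of cause at every scan, plus any later event attributed to the drug.
- *Over half of MRI harms are missed.* 420 / (420 + 380) = 52.5% is a share of planned sessions, not of harms. The 380 baseline MRIs include 150 Confirmatory subjects with no follow-up MRI, and a recent comparable MRI may replace the screening one.
- *The events are lost.* They go to medical history, which is updated at months 5, 9, 14 and 18.

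**Conclusion.** The point holds as an inconsistency in non-serious adverse event recording at the exploratory follow-up visits. Read as written, 7.7.2 and SAP 6.6.2 treat the same procedure harm differently at baseline and at months 9 and 18, and they conflict with broader statements elsewhere in the protocol.

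Its size is bounded by about 420 MRI sessions. This assumes full planned enrolment, two follow-up MRIs per subject and no dropout; sessions covered by the 48 hours after injection come off that number. The number of events cannot be estimated, because the documents give no event rate for MRI or other procedures. No efficacy result, tracer-safety result or currently planned adverse event summary changes. The case for acting rests on the protocol's own aim of capturing effects of trial participation and on the low cost of the correction.

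**What to change.** 1. In Protocol 7.7.2, widen the exception for events outside the 48 hours to those attributable to the drug *or a protocol procedure*, as 7.7.4 does for serious events.
2. Define month-9 and month-18 follow-up imaging periods, from the first follow-up procedure to 48 hours after the last, in which trial-emergent events are reported as at baseline. This also gives meaning to the period that 7.7.2 mentions but does not define.
3. Align the end of adverse event reporting in 7.7.2 so that a month-18 procedure done after the last scan is covered.
4. Reconcile 10.7 and the flow-chart rows with the revised 7.7.2, and carry the definitions into SAP 6.6.2.
5. Add a trial-emergent summary to SAP 8.7.2, or state there that these events are listed. Without this step the newly recorded events would enter no summary.

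The cost is amendment wording, slightly more adverse event recording by sites, and one more table or listing. The flow chart already marks adverse event collection at the exploratory follow-up visits, so no new visit or assessment is needed.
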